APPENDIX 2 GEOGRAPHIC REGIONS

Geographic Region	Countries
North America	United States Puerto Rico Mexico
South America	Chile Colombia Peru
Europe	France Germany Netherlands Russia Greece Romania Hungary Italy Poland South Africa
Oceania	Australia

APPENDIX 3 MARKED LABORATORY ABNORMALITIES CRITERIA

Laboratory parameter	Code	Low Criterion		High Criterion	
		US units	SI units	US units	SI units
Hemoglobin	HB	< BASELINE - 0.3 g/dL	< BASELINE -3 g/L		
		< 7 G/DL	< 70 G/L		
Hematocrit	HCT	< 0.75*BASELINE			
Erythrocytes	RBC	< 0.75*BASELINE			
Platelet Count	PLAT	< 0.5*BASELINE AND <100 x10 ⁹ c/L IF BASELINE < LLN	<100 x10 ⁹ c/L	>1.5*ULN IF LLN <= BASELINE <= ULN	
		<0.67*LLN IF LLN <= BASELINE <= ULN			
		<50 x10 ⁹ c/L			
Leukocytes	WBC	<0.75*LLN IF LLN <= BASELINE <= ULN		> 1.25*ULN IF LLN <= BASELINE <= ULN	
		<0.8*BASELINE IF BASELINE < LLN		>ULN IF BASELINE < LLN	
		< LLN IF BASELINE > ULN		> 1.2*BASELINE IF BASELINE > ULN	
		<2.0 x10 ³ c/uL	<2.0 x10 ⁹ c/L		
Neutrophils + Bands (absolute)	PMNBA	<1.000 x10 ³ c/uL	<1.000 x10 ⁹ c/L		
Eosinophils (absolute)	EOSA			> 0.750 x10 ³ c/uL	> 0.750 x10 ⁹ c/L
Basophils (absolute)	BASOA			>0.400 x10 ³ c/uL	>0.400 x10 ⁹ c/L
Monocytes (absolute)	MONOA			> 2.000 x10 ³ c/uL	> 2.000 x10 ⁹ c/L
Lymphocytes (absolute)	LYMPA	< 0.750 x10 ³ c/uL	< 0.750 x10 ⁹ c/L	> 7.500 x10 ³ c/uL	> 7.500 x10 ⁹ c/L
		<0.5 x10 ³ c/uL	<0.5 x10 ⁹ c/L		
Blasts (relative)	BLAST			>0 %	>0
PT Ratio	PTR			> 1.33*BASELINE	
aPTT Ratio	APTTR			> 1.33*BASELINE	
Intl Normalized Ratio	INR			> 1.33*BASELINE	
Alkaline Phosphatase	ALP			> 2*ULN IF LLN <= BASELINE <= ULN	
				> 3*BASELINE IF BASELINE > ULN	

Laboratory parameter	Code	Low Criterion		High Criterion	
		US units	SI units	US units	SI units
				>5.0 xULN	
Aspartate Aminotransferase	AST			> 3*ULN IF LLN <= BASELINE <= ULN	
				> 4*BASELINE IF BASELINE > ULN	
				>5.0 xULN	
Alanine Aminotransferase	ALT			> 3*ULN IF LLN <= BASELINE <= ULN	
				> 4*BASELINE IF BASELINE > ULN	
				>5.0 xULN	
G-Glutamyl Transferase	GGT			> 2*ULN IF LLN <= BASELINE <= ULN	
				> 3*BASELINE IF BASELINE > ULN	
Bilirubin, Total	TBILI			> 2*ULN IF LLN <= BASELINE <= ULN	
				> 4*BASELINE IF BASELINE > ULN	
				>3.0 xULN	
Bilirubin, Direct	DBILI			> 1.5*ULN IF LLN <= BASELINE <= ULN	
				> 2*BASELINE IF BASELINE > ULN	
Blood Urea Nitrogen	BUN			> 2*BASELINE	
Creatinine	CREAT			> 1.5*BASELINE	
				>3.0 xULN	
Protein/Creatinine Ratio	PRCRR			> 4 mg/mg	> 4519.8 mg/mmol
Creatinine Clearance	CRCL	< 0.67*BASELINE			
Sodium, Serum	NA	< 0.95*LLN IF LLN <= BASELINE <= ULN		> 1.05*ULN IF LLN <= BASELINE <= ULN	
		< 0.95*BASELINE IF BASELINE < LLN		> ULN IF BASELINE < LLN	
		< LLN IF BASELINE > ULN		> 1.05*BASELINE IF BASELINE > ULN	
		< 130 mEq/L	< 130 mmol/L	> 155 mEq/L	> 155 mmol/L

Laboratory parameter	Code	Low Criterion		High Criterion	
		US units	SI units	US units	SI units
Potassium, Serum	K	$< 0.9 * LLN$ IF $LLN \leq$ BASELINE \leq ULN		$> 1.1 * ULN$ IF $LLN \leq$ BASELINE \leq ULN	
		$< 0.9 * BASELINE$ IF BASELINE $<$ LLN		$> ULN$ IF BASELINE $<$ LLN	
		$< LLN$ IF BASELINE $>$ ULN		$> 1.1 * BASELINE$ IF BASELINE $>$ ULN	
		< 2.5 mEq/L	< 2.5 mmol/L	> 6.0 mEq/L	> 6.0 mmol/L
Chloride, Serum	CL	$< 0.9 * LLN$ IF $LLN \leq$ BASELINE \leq ULN		$> 1.1 * ULN$ IF $LLN \leq$ BASELINE \leq ULN	
		$< 0.9 * BASELINE$ IF BASELINE $<$ LLN		$> ULN$ IF BASELINE $<$ LLN	
		$< LLN$ IF BASELINE $>$ ULN		$> 1.1 * BASELINE$ IF BASELINE $>$ ULN	
		$< LLN$ IF BASELINE $>$ ULN		$> 1.1 * BASELINE$ IF BASELINE $>$ ULN	
Carbon Dioxide, Total	CO2	$< 0.75 * LLN$ IF $LLN \leq$ BASELINE \leq ULN		$> 1.25 * ULN$ IF $LLN \leq$ BASELINE \leq ULN	
		$< 0.75 * BASELINE$ IF BASELINE $<$ LLN		$> ULN$ IF BASELINE $<$ LLN	
		$< LLN$ IF BASELINE $>$ ULN		$> 1.25 * BASELINE$ IF BASELINE $>$ ULN	
		$< LLN$ IF BASELINE $>$ ULN		$> 1.25 * BASELINE$ IF BASELINE $>$ ULN	
Bicarbonate	HCO3	$< 0.75 * LLN$ IF $LLN \leq$ BASELINE \leq ULN		$> 1.25 * ULN$ IF $LLN \leq$ BASELINE \leq ULN	
		$< 0.75 * BASELINE$ IF BASELINE $<$ LLN		$> ULN$ IF BASELINE $<$ LLN	
		$< LLN$ IF BASELINE $>$ ULN		$> 1.25 * BASELINE$ IF BASELINE $>$ ULN	
		$< LLN$ IF BASELINE $>$ ULN		$> 1.25 * BASELINE$ IF BASELINE $>$ ULN	
Calcium	CA	$< 0.8 * LLN$ IF $LLN \leq$ BASELINE \leq ULN		$> 1.2 * ULN$ IF $LLN \leq$ BASELINE \leq ULN	
		$< 0.75 * BASELINE$ IF BASELINE $<$ LLN		$> ULN$ IF BASELINE $<$ LLN	
		$< LLN$ IF BASELINE $>$ ULN		$> 1.25 * BASELINE$ IF BASELINE $>$ ULN	
		< 7 mg/dL	< 1.75 mmol/L	> 12.5 mg/dL	> 3.13 mmol/L
Phosphorus, Inorganic	PHOS	$< 0.75 * LLN$ IF $LLN \leq$ BASELINE \leq ULN		$> 1.25 * ULN$ IF $LLN \leq$ BASELINE \leq ULN	
		$< 0.67 * BASELINE$ IF BASELINE $<$ LLN		$> ULN$ IF BASELINE $<$ LLN	
		$< LLN$ IF BASELINE $>$ ULN		$> 1.33 * BASELINE$ IF BASELINE $>$ ULN	
		< 2.0 mg/dL	< 0.65 mmol/L		
Magnesium,	MG	$< 0.6 * LLN$ IF $LLN \leq$ BASELINE \leq ULN		$> 2.0 * ULN$ IF $LLN \leq$ BASELINE \leq ULN	

Laboratory parameter	Code	Low Criterion		High Criterion	
		US units	SI units	US units	SI units
Serum		ULN		<= ULN	
		< 0.67*BASELINE IF BASELINE < LLN		>ULN IF BASELINE < LLN	
		<LLN IF BASELINE > ULN		> 2.0*BASELINE IF BASELINE > ULN	
Glucose, Serum	GLUC	< 65 mg/dL	< 3.6 mmol/L	> 220 mg/dL	> 12.2 mmol/L
Glucose, Fasting Serum	GLUCF	< 0.8*LLN IF LLN <= BASELINE <= ULN		> 1.5*ULN IF LLN <= BASELINE <= ULN	
		< 0.8*BASELINE IF BASELINE < LLN		>ULN IF BASELINE < LLN	
		< LLN IF BASELINE > ULN		> 2.0*BASELINE IF BASELINE > ULN	
Protein, Total	TPRO	< 0.9*LLN IF LLN <= BASELINE <= ULN		> 1.1*ULN IF LLN <= BASELINE <= ULN	
		< 0.9*BASELINE IF BASELINE < LLN		>ULN IF BASELINE < LLN	
		<LLN IF BASELINE > ULN		> 1.1*BASELINE IF BASELINE > ULN	
Albumin	ALB	< 0.9*LLN IF LLN <= BASELINE <= ULN			
		< 0.75*BASELINE IF BASELINE < LLN			
		< 2 g/dL	< 20 g/L		
Cholesterol, Total	CHOL			> 2*BASELINE	
Triglycerides, Fasting	TRIGF			≥ 2.0*ULN IF LLN <= BASELINE <= ULN	
				> 2.0*BASELINE IF BASELINE > ULN	
Amylase, Total	AMYL			> 3*ULN IF LLN <= BASELINE <= ULN	
				> 4*BASELINE IF BASELINE > ULN	
Creatinine Phosphokinase	CK			> 4*BASELINE	
Uric Acid	URIC			> 1.5*ULN IF LLN <= BASELINE <= ULN	
				> 2*BASELINE IF BASELINE > ULN	
Lactate Dehydrogenase	LD			> 1.5*ULN IF LLN <= BASELINE <= ULN	

Laboratory parameter	Code	Low Criterion		High Criterion	
		US units	SI units	US units	SI units
Protein, Urine	UPRO			> 3*BASELINE IF BASELINE > ULN	
				>= 2 IF MISSING BASELINE VA >= 4	
				>= 2 IF 0=< BASELINE =<0.5	
				>= 3 IF BASELINE = 1	
Glucose, Urine	UGLU			>= 4 IF 2=< BASELINE =<3	
				>= 2 IF MISSING BASELINE VA >= 4	
				>= 2 IF 0=< BASELINE =<0.5	
				>= 3 IF BASELINE = 1	
Ketones, Urine	UKET			>= 4 IF 2=< BASELINE =<3	
				>= 2 IF MISSING BASELINE	
				>= 4	
				>= 2 IF 0=< BASELINE =<0.5	
Blood, Urine	UBLD			>= 3 IF BASELINE = 1	
				>= 4 IF 2=< BASELINE =<3	
				>= 2 IF MISSING BASELINE	
				>= 4	
Leukocyte Esterase, Urine	ULEUK			>= 2 IF 0=< BASELINE =<0.5	
				>= 3 IF BASELINE = 1	
				>= 4 IF 2=< BASELINE =<3	
				>= 2 IF MISSING BASELINE	
RBC, Urine	URBC			>= 4 hpf	
				>= 2 hpf IF MISSING BASELINE	
				>= 2 hpf IF 0=< BASELINE =<0.5 hpf	
				>= 3 hpf IF BASELINE = 1 hpf	
WBC, Urine	UWBC			>= 4 hpf IF 2 hpf =< BASELINE =<3 hpf	
				>= 2 hpf IF MISSING BASELINE	

Laboratory parameter	Code	Low Criterion		High Criterion	
		US units	SI units	US units	SI units
					>= 4 hpf
				>= 2 hpf IF 0=< BASELINE =<0.5 hpf	
				>= 3 hpf IF BASELINE = 1 hpf	
				>= 4 hpf IF 2 hpf =< BASELINE =<3 hpf	

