Protein Glucose Blood Leukocyte esterase Specific gravity pH Reflex to microscopic examination of the sediment if blood, protein or leukocytes esterase are positive on the dipstick Spot urine protein/creatinine ratio [UPCR] (screening only, in subjects with clinical suspicion of nephrotic syndrome or clinically significant protein on urinalysis)
Serology
Serum for hepatitis C antibody, hepatitis B surface antigen, hepatitis B core antibody (screening only) HIV testing (screening only, may be performed locally or via central lab per local requirements) Auto-immune serology: ANA, Anti-SSA/Ro, Anti-SSB/La, Rheumatoid Factor Immunoglobulin levels: IgM, IgA, and IgG Complement levels (C3, C4, CH50)
Other Analyses
IGRA/TB Test
Pregnancy test (WOCBP only; urine test, serum test only to be performed if urine test is positive or uninterpretable, or if necessary as per local/institutional requirements).
Follicle stimulating hormone (FSH): (screening only, for post-menopausal women only, see Section 3.3.3)

Results of all laboratory tests required by this protocol must be provided to BMS, either recorded on the laboratory pages of the CRF or by another mechanism as agreed upon between the investigator and BMS (eg, provided electronically). If the units of a test result differ from those printed on the CRF, the recorded laboratory values must specify the correct units. Any abnormal laboratory test result considered clinically significant by the investigator must be recorded on the appropriate AE page of the CRF (see [Section 6.1.1](#)).

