7.6.2 Laboratory evaluation

Unless otherwise specified, laboratory data obtained after the start of study medication dosing up to and including 42 days after the last double-blind dosing date will be considered as obtained during the double-blind treatment period.

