7.6.2.1 Marked Laboratory Abnormalities

Laboratory marked abnormality using pre-defined abnormality criteria will also be descriptively summarized (see [APPENDIX 3](#)). The results of all protocol-specified clinical laboratory tests, as well as laboratory results outside of the normal range, will be listed.

The frequency of subjects with any marked laboratory abnormality will be presented by laboratory test during the double-blind treatment period. The results are based on the As-treated analysis population.

The criteria used for classifying laboratory test results as markedly abnormal will be listed.

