8.22 United States Conventional Units and Standard International Units for Laboratory Data

Unless otherwise specified, all analyses of laboratory data (independently of being safety or efficacy) will be performed in both United States Conventional Units (US) and Standard International Units (SI). Conversion between US and SI, and vice versa, will be performed using the BMS standard conversion factors.

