8.23 Laboratory evaluations

All laboratory evaluations performed by central laboratories and local laboratories that are included in the database will be included in summary tables and in the listings.

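### SAP Appendix 3: the SI threshold for the urine protein/creatinine ratio is a tenfold conversion error, with little or no effect expected on the planned tables

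*SAP*

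**What the plan says.** SAP Appendix 3 lists, for each laboratory parameter, the limits beyond which a result counts as markedly abnormal. For the protein/creatinine ratio there is only a high criterion: more than 4 mg/mg in the US column and "> 4519.8 mg/mmol" in the SI column.

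Four other places decide what this row does:

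- SAP 8.22 says that, unless otherwise specified, laboratory analyses "will be performed in both United States Conventional Units (US) and Standard International Units (SI", with conversion by the sponsor's standard factors. Those factors are not given.
- SAP 7.6.2.1 applies the criteria: "The frequency of subjects with any marked laboratory abnormality will be presented by laboratory test during the double-blind treatment period". It also says that the criteria themselves, and the results of the tests the protocol specifies, will be listed.
- SAP 7.6.2 assigns to the double-blind period "laboratory data obtained after the start of study medication dosing up to and including 42 days after the last double-blind dosing date".
- Protocol 5.3.2, within Safety Assessments, has the test as "Spot urine protein/creatinine ratio [UPCR] (screening only, in subjects with clinical suspicion of nephrotic syndrome or clinically significant protein on urinalysis".

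SAP 8.23 adds: "All laboratory evaluations performed by central laboratories and local laboratories that are included in the database will be included in summary tables". The same holds for listings.

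**The concern.** The two columns of a row should give one limit in two unit systems, so that a result is classified the same way in both. Here they do not. If a post-dose ratio lay between the two limits, the US table would count the subject as markedly abnormal and the SI table would not.

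Renal involvement is an ESSDAI domain, and nephrotic syndrome is named in the exclusion criteria. A contradictory proteinuria criterion in the safety appendix is therefore worth correcting even if it is rarely used. The mismatched pair would also appear in the planned listing of criteria whether or not any ratio is flagged.

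There is a second possibility. If the printed limit came from a wrong conversion factor and not from a typing slip, converted values of this parameter could be tenfold wrong too.

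**Working it through.** **Inputs.** US limit 4 mg/mg and SI limit 4519.8 mg/mmol (SAP Appendix 3). Creatinine molar mass: not in the documents; assumed 113.12 g/mol, that is 113.12 mg per mmol, with 112.9 to 113.2 as the range.

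**Formula.** Ratio in mg/mmol = ratio in mg/mg × mg of creatinine per mmol.

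**Can the printed figure be reproduced?** Only with a factor of 4519.8 / 4 = 1129.95 mg per mmol, ten times the molar mass. As a divisor, 4 / 0.000885 = 4519.8, whereas 4 / 0.00885 = 451.98. The latter is one tenth of the printed figure, which suggests a misplaced decimal point, in either the threshold or the factor.

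**Correct conversion and size of the error.**

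| Molar mass (g/mol) | 4 mg/mg in mg/mmol | Printed limit in mg/mg | Printed / correct |
|---|---|---|---|
| 112.9 | 451.6 | 40.03 | 10.01 |
| 113.12 | 452.5 | 39.96 | 9.99 |
| 113.2 | 452.8 | 39.93 | 9.98 |

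**Example.** A ratio of 10 mg/mg is 10 × 113.12 = 1131 mg/mmol: above the US limit and below the printed SI limit.

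**Other rows with absolute limits in both systems** (usual conversion factors, also assumed):

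- Calcium: 7 mg/dL / 4.008 = 1.75 mmol/L, as printed. 12.5 / 4.008 = 3.12 against 3.13 printed; a rounded divisor of 4 gives 3.125.
- Glucose: 65 and 220 mg/dL / 18.016 = 3.6 and 12.2 mmol/L, as printed.
- Phosphorus: 2.0 mg/dL / 3.0974 = 0.65 mmol/L, as printed.
- Hemoglobin: 0.3 and 7 g/dL × 10 = 3 and 70 g/L, as printed.
- Albumin: 2 g/dL × 10 = 20 g/L, as printed.

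Of the rows checked, only the protein/creatinine ratio is out by a factor of ten.

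**Can the row act on planned data?** The scheduled ratio is taken before randomization. The marked-abnormality table opens only after dosing starts. SAP 8.3 closes the safety-laboratory window at 28 days after the last lulizumab or matching placebo dose, where SAP 7.6.2 says 42, but neither reaches back to screening. The ratio is also absent from the parameters summarized over time in SAP 7.6.2.2. So no scheduled ratio enters the table in either unit system.

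**The case against.** A reader might infer that the SI safety table will miss heavy proteinuria that the US table flags. The documents do not support that as an unconditional statement, and the case against it is strong:

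- With a selective, screening-only test, neither planned table contains the ratio, so the two cannot disagree on scheduled data.
- SAP 8.23 brings in only results already in the database. Protocol 5.3 tells sites to submit only protocol-specified assessments on the case report form and to keep standard-of-care results in the medical record unless the sponsor asks for them. An on-treatment ratio ordered locally would normally stay there.
- Proteinuria is watched by other means. Urinalysis protein is part of the scheduled safety laboratory tests during treatment and at Week 18, and has its own marked-abnormality criterion (UPRO), which does not depend on this conversion. Clinically significant laboratory results are recorded as adverse events whatever the SAP flag says. The US-unit table would still flag any ratio above 4 mg/mg.

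All of this stands, and it limits the consequence. It does not remove the error. An unscheduled result can still enter by sponsor request (Protocol 5.3) or on a supplemental case report form (Protocol 6.2.1), and SAP 8.23 would then put it in the tables.

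It could also be said that the molar mass is an outside constant and the sponsor's factors are not shown. That is true, but no plausible factor closes a tenfold gap. It is likewise tempting to say that the SI criterion could in practice never be met; the documents give no data on how often ratios exceed 40 mg/mg, so that cannot be claimed.

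**Conclusion.** The SI limit is wrong as written by a factor of ten (9.98 to 10.01 over the molar masses tried): it corresponds to about 40 mg/mg where the US column has 4 mg/mg. The arithmetic rests on one outside constant and is insensitive to it.

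Little or no effect on the planned tables is expected. Disagreement between the US and SI tables requires an unscheduled on-treatment ratio between about 4 and 40 mg/mg that reaches the database. For such a result the US table would still flag it, and UPRO remains as a separate on-treatment check for proteinuria. The documents do not show whether the slip is in the printed limit alone or also in the programmed factor. In the latter case the listed screening ratios could also be wrong in SI units. This is a minor correction.

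**What to change.** In SAP Appendix 3, make the SI limit for the protein/creatinine ratio agree with 4 mg/mg: about 452 mg/mmol, or the exact value from the sponsor's standard factor. Verify the conversion factor programmed for this parameter, so that converted values and the limit are on the same scale. It would also help to state whether the row is meant to apply on treatment, since the protocol schedules the test at screening only.

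The cost is one number in the SAP, one factor to check and, if wanted, one clarifying sentence. No data collection or analysis method changes.

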APPENDIX 4 DOCUMENT HISTORY

Version	Statistician	Date	Notes/Revisions
1.0	[name]	30 October 2016	Original version
